#### Statistical methods:

The sample calculation has been done for the **primary endpoint (cohort 1)** and it's based on a Fleming's Single Stage Procedure:

We want to show that the Intracranial response rate by modified RECIST 1.1 before local treatment is superior or equal to the reference value, say, 90=40%. Under the hypothesis to have a response rate under new treatment ( $\pi$ 1) of 60% with  $\alpha$  risk = 5% in one-sided test and a power of 80%, the required sample size is 38 patients.

Finally, if 20% of patients will be lost of follow up, die or progress before day 56 without doing the first tumour assessment (according data published in COMBI-MB study), the initial sample size will be 48 patients, to obtain 38 evaluable patients.

Data of study will be analysed in the following populations:

- ITT: All patients that has been enrolled in the trial
- Evaluable population (PP): All patients fulfilling all eligibility criteria and having at least two valid tumour assessments (baseline and one evaluation MRI or CT-scan) without any protocol deviation that makes the patient invalid for the primary endpoint evaluation.
- Safety population: All patients receiving at least one dose of treatment.

Cohort 2 (N=15) is exploratory and no formal sample calculation has been performed, a descriptive analysis will be performed on the same variables and population as cohort 1 (N=48). The only difference is that the population included will be symptomatic. The efficacy and safety as an overall of both cohorts in conjunction will be also addressed.				

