Thus, COMBI-MB supports the use of dabrafenib and trametinib also in BRAF mutant melanoma patients with brain metastases. However, one of the main critics to this study, is the apparently short progression free survival in the main cohort (cohort A, patients asymptomatic) in comparison with patients treated in other clinical trials with the same combination and no brain metastases: 5.6 months in COMBI MB versus 11 months in COMBI-D. One of the reasons could be the well-known poorer prognosis of these patients, but another one could be the fact that patients in this clinical trial, were not allowed by protocol to be treated with a local therapy (except for previously treated ones in cohort B, C and D, but always before the dabrafenib and trametinib). For those patients achieving a non-complete response, it is unknown if further local therapy (radiation, radiosurgery, surgery) could improve the duration of the responses.

Combination or sequencing of systemic (targeted) and local treatment with radiation has demonstrated a manageable toxicity profile, with some concerns regarding radio necrosis and increase in dermatitis. Most of these data, however, come from retrospective case series.

Finally, although encorafenib in combination with binimetinib is indicated for the treatment of adult patients with unresectable or metastatic melanoma with a BRAF V600 mutation, it is unknown the activity in patients with BRAF mutant melanoma and brain metastases.

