# 10. STATISTICS

# 10.1. Sample size calculation

# Sample size calculation:

The sample calculation has been done for the **initially proposed primary endpoint (cohort 1)** and it's based on a Fleming's Single Stage Procedure:

We want to show that the Intracranial response rate by modified RECIST 1.1 before local treatment is superior or equal to the reference value, say, 90=40%. Under the hypothesis to have a response rate under new treatment ( $\pi$ 1) of 60% with  $\alpha$  risk = 5% in one-sided test and a power of 80%, the required sample size is 38 patients.

Finally, assuming that, 20% of patients will be lost of follow up, die or progress before day 56 without doing the first tumour assessment (according data published in COMBI-MB study), the initial sample size will be 48 patients, to obtain 38 evaluable patients.

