# 3. RESULTS

# 3.1. RECRUITED PATIENTS

All baseline characteristics will be performed using the ITT and PP population. In order to report the main efficacy analysis, also both the ITT and PP population will be used, meanwhile the secondary efficacy endpoints will be analyzed using the PP population. Finally the safety population will be used to report the safety results.

Table 8: Patients recruited by Hospital

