# 4. PRIMARY EFFICACY OBJECTIVE

# 4.1. ITT PRIMARY EFFICACY OBJECTIVE: RESPONSE AT 56 DAYS

Table 39: Primary Efficacy Objective. Day 56 Evaluation. ITT

intracranial Evaluation at 56 days	
CR	
PR	
SD	
PD	
NE	

Table 40: ITT: intracranial Objective Response Rate at 56 days

All patients: ORR intracranial response	
CR or PR	

All patients: ORR intracranial response	
SD or PD	
NE	
Total	
Cohort 1: ORR intracranial response	
CR or PR	
SD or PD	
NE	
Total	
Cohort 2: ORR intracranial response	
CR or PR	
SD or PD	
Total	

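### The stated 80% power holds only for evaluable patients; for the ITT response rate, also a main analysis, the plan's own inputs give exact power of about 24% (cohort 1) or 28% (pooled)

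*Combined protocol and SAP*

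**What the plan says.** Protocol section 10.1, on a Fleming single-stage design for what it calls the initially proposed cohort 1 endpoint, tests 60% against 40% with "risk = 5% in one-sided test and a power of 80%, the required sample size is 38 patients". It then allows for attrition: "20% of patients will be lost of follow up, die or progress before day 56 without doing the first tumour assessment". The synopsis repeats this and concludes that "the initial sample size will be 48 patients, to obtain 38 evaluable patients". Under protocol section 10.2 the current primary endpoint is the intracranial response rate in cohorts 1 and 2 together (48 + 15 = 63), also reported by cohort.

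SAP section 2 defines ITT as everyone included except screening failures. PP requires eligibility, a baseline assessment and a first assessment. On which set carries the primary result, SAP section 3.1 says: "In order to report the main efficacy analysis, also both the ITT and PP population will be used". Neither set is named as decisive. In SAP section 4.1, "Table 40: ITT: intracranial Objective Response Rate at 56 days" has rows for CR or PR, SD or PD, NE and Total, both for all patients and for cohort 1.

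**The concern.** Death or progression before the first scan is a failure of the endpoint, not neutral missing data, yet section 10.1 handles it in the same allowance as loss to follow-up. Enrolling 48 instead of 38 restores the number of scanned patients. It does not restore the effect size once the unscanned patients return to the denominator.

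At stake is the only power figure in the plan. A reader will take 80% as applying to the main efficacy result, but that result is reported on two sets, and the figure was derived for only one of them. With the regimen performing exactly as hypothesised, a one-sided 5% test would probably succeed on PP and not on ITT, and the plan does not prepare anyone for that.

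**Working it through.** **Inputs.** Null 40%, alternative 60%, one-sided 5%, power 80%, 38 evaluable, 20% without a first assessment, 48 enrolled (protocol 10.1). Pooled N = 63 (synopsis). Unassessed patients count as ITT non-responders (inferred from the ITT definition and Table 40).

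**The plan's own figures.** Normal approximation: n = [(1.645√(0.40 × 0.60) + 0.842√(0.60 × 0.40)) / (0.60 − 0.40)]² = 37.1, so 38. Inflation: 38 / 0.80 = 47.5, so 48. Both reproduce.

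**Power for 38 evaluable patients.**
- Normal: Φ[(0.20√38 − 1.645√0.24) / √0.24] = Φ(0.872) = 80.8%.
- Exact: the smallest count r with P(X ≥ r | 38, 0.40) ≤ 0.05 is 21 (alpha 4.1%), and P(X ≥ 21 | 38, 0.60) = 77.8%.

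**Expected ITT rate.** 0.80 × 0.60 + 0.20 × 0 = 0.48.

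**ITT power at 48%, cohort 1, N = 48.**
- Exact: r = 26 (alpha 3.3%), and P(X ≥ 26 | 48, 0.48) = 23.9%.
- Normal: Φ[(0.08√48 − 1.645√0.24) / √(0.48 × 0.52)] = Φ(−0.50) = 30.7%.

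**ITT power at 48%, pooled, N = 63, with the same 60% and 20% assumed in cohort 2.**
- Exact: r = 33 (alpha 3.1%), power 28.4%.
- Normal: Φ[(0.08√63 − 1.645√0.24) / √(0.48 × 0.52)] = Φ(−0.34) = 36.6%.

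**Sensitivity to the unassessed share u**, with ITT rate 0.60 × (1 − u), exact:

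| u | ITT rate | Cohort 1, ≥26/48 | Pooled, ≥33/63 |
|---|---|---|---|
| 0% | 60% | 83.5% | 91.3% |
| 5% | 57% | 70.8% | 80.8% |
| 10% | 54% | 55.0% | 65.1% |
| 15% | 51% | 38.5% | 46.3% |
| 20% | 48% | 23.9% | 28.4% |

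**Scale.** For 80% power at 48% against 40%, the normal formula gives [(1.645√0.24 + 0.842√0.2496) / 0.08]² = 235 patients (242 exact). An allowance of ten patients cannot close that gap.

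**The case against.** **Counting NE as non-response is inferred, not written.** Protocol section 10.7 says analyses use what was observed, without replacing dropouts. The evidence is an empty table shell. The PP shell (Table 42) also has NE rows although PP requires a first assessment, and the cohort 2 block of Table 40 has none. This stands as a caveat and is itself a reason to write the rule down. Excluding unassessed patients would in effect make ITT the same as PP.

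**No ITT test is specified.** The SAP response tables show no threshold, and protocol section 10.6 plans point estimates with exact 95% intervals. Section 4.1 calls the study positive if the rate is at least 40%. Read as a point-estimate rule, a true 48% passes 85% of the time (≥20/48) or 88% (≥26/63), but type I error is about 46% or 47%. So the low ITT power belongs to the section 10.1 test, the only rule with stated operating characteristics. The documents do not establish that the trial would be declared negative on ITT.

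**Perhaps 60% was meant for all enrolled patients.** ITT power would then be 83.5% at N=48, but inflating 38 to 48 would serve no purpose, and 20% unassessed would require 0.60 / 0.80 = 75% among assessed patients. Nothing in the documents supports that.

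Three stronger readings are tempting and not supported:
- *A fall from 80% to 24%.* This mixes methods. Like for like it is 78% to 24% exact, or 81% to 31% normal.
- *Early failures alone use up the 20%.* A reader might infer this from the PFS of "5.6 months in COMBI MB" in section 3, since an exponential curve gives about 20% by day 56. But the allowance covers patients without a first assessment, whereas PFS also counts progression found at that scan. The exponential shape is not in the documents, and the figure is not stated to be intracranial.
- *The PP test has a type I error above 30%.* This requires redefining the null as 40% of all enrolled patients. On the evaluable basis of section 10.1, exact alpha is 4.1%.

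**Conclusion.** The concern holds in a limited form. The sample-size arithmetic is correct; the fault is the scope of the power statement, which describes the evaluable (PP) analysis and not the ITT analysis reported beside it. The low ITT figures rest on three assumptions: 60% is the rate among evaluable patients, 20% have no first assessment, and those patients are non-responders in ITT. The first two come from section 10.1, the first by implication; the third is inferred. The pooled figure also carries the cohort 1 assumptions over to cohort 2. The conclusion does not depend on the full 20%: with 10% unassessed, cohort 1 ITT power is still only 55%.

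**What to change.** 1. In protocol section 10.1 and the synopsis, state that the 80% power (77.8% exact, success at ≥21/38) is for evaluable patients only and does not hold for ITT.
2. In the SAP, state that patients with no first assessment, including early death or progression, count as non-responders in the ITT rate. Loss to follow-up falls under the same rule, because an all-included denominator leaves no separate allowance for it.
3. Give the ITT thresholds, ≥26/48 (exact alpha 3.3%) and ≥33/63 (3.1%), with power across the range of unassessed shares tabulated above.
4. Do not relabel 60% as an all-enrolled rate unless the sponsor can justify it; otherwise the power is restored only on paper.

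The cost is wording in the protocol, synopsis and SAP. No procedure changes and no extra patients are proposed. The downside is that the plan must admit low ITT power if the stated inputs hold.

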# 10.2. Study endpoints

Intracranial objective response (iORR) rate by modified RECIST 1.1 before local treatment in cohort 1 and 2: iORR calculated as the proportion of patient with a best overall intracranial response of complete response (CR) or partial response (PR) before local treatment in cohort 1 and 2. The final statistical analysis of this endpoint is expected to be performed within 3 months after the local treatment of the last patient in any cohort. iORR will be also reported separately for both cohorts.

**Duration of intracranial response in both cohorts (iDOR):** Calculated as the time from the date of first documented CR or PR to the first documented intracranial progression or death due to underlying cancer, in patients with documented intracranial CR or PR before local treatment. The final statistical analysis of this endpoint is expected to be performed within 6 months after database closure expected at 24 months after last patient inclusion, however interim analysis might be performed when analysing other primary variables.

The intracranial progression free survival (iPFS) by modified RECIST in both cohorts: iPFS is defined as the time from the date of inclusion to the date of the first documented intracranial disease progression or death due to any cause, whichever occurs first. PFS will be determined based on tumour assessment (modified RECIST version 1.1 criteria). The local Investigator's assessments will be used for analyses. Those patients who are alive and have not progressed at the last follow-up, date of progression will be censored at the date of the last follow-up. Patient with no additional image test other than baseline will be censored to the day after to inclusion. The final statistical analysis of this endpoint is expected to be performed within 6 months after database closure expected at 24 months after last patient inclusion, however interim analysis might be performed when analysing other primary variables.

Percentage of patients free of intracranial progression at 6 (week 24), 12 (week 48) and 24 months (week 96) in both cohorts: percentage of patients free of intracranial progression assessed by modified RECIST at 6 months (week 24), 12 months (week 48) and 24-month (week 96) considering date of inclusion. The final statistical analysis of this endpoint is expected to be

performed within 6 months after database closure expected at 24 months after last patient inclusion, however interim analysis might be performed when analysing other primary variables

Percentage of patients (%) free of extracraneal progression at 6 (week 24), 12 (week 28) and 24 months (week 96): percentage of patients free of progression by RECIST 1.1 at 6 months (week 24), 12 months (week 48) and 24-month (week 96) considering date of inclusion. The final statistical analysis of this endpoint is expected to be performed within 6 months after database closure expected at 24 months after last patient inclusion, however interim analysis might be performed when analysing other primary variables.

**Overall Survival in both cohorts (OS):** OS is calculated as the time from date of inclusion to date of death due to any cause. The final statistical analysis of this endpoint is expected to be performed within 6 months after database closure expected at 24 months after last patient inclusion, however interim analysis might be performed when analysing other primary variables.

Percentage of patients (%) alive at 6, 12 and 24 months in both cohorts: percentage of patients alive at 6 months, 12 month and 24-month considering date of inclusion. The final statistical analysis of this endpoint is expected to be performed within 6 months after database closure expected at 24 months after last patient inclusion, however interim analysis might be performed when analysing other primary variables.

**Toxicity of the combination until local treatment:** Number of patients with adverse events and serious adverse events, changes in laboratory values, vital signs, electrocardiograms (ECGs), LVEF (MUGA (Multigated Acquisition Scan) / echocardiogram) and assessment of physician, dermatological and ocular examinations graded according to the National Cancer Institute (NCI) Common Terminology Criteria for Adverse Events (CTCAE) v 4.03 until local treatment (local treatment D1). It will be studied using descriptive statistics techniques, such as frequency tables and contingency tables. The final statistical analysis of this endpoint is expected to be performed within 6 months after database closure expected at 24 months after last patient inclusion, however interim analysis might be performed when analysing other primary variables.

**Toxicity of the combination after local treatment:** Number of patients with adverse events and serious adverse events, changes in laboratory values, vital signs, electrocardiograms (ECGs), LVEF (MUGA (Multigated Acquisition Scan) / echocardiogram) and assessment of physician, dermatological and ocular examinations graded according to the National Cancer Institute (NCI) Common Terminology Criteria for Adverse Events (CTCAE) v 4.03 after local treatment (after end of local treatment date). It will be studied using descriptive statistics techniques, such as frequency tables and contingency tables. The final statistical analysis of this endpoint is expected to be performed within 6 months after database closure expected at 24 months after last patient inclusion, however interim analysis might be performed when analysing other primary variables.

**Quality of life:** Change from baseline in the global health status score of the EORTC QLQ-C30. The final statistical analysis of this endpoint is expected to be performed within 6 months after database closure expected at 24 months after last patient inclusion, however interim analysis might be performed when analysing other primary variables.

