#### 10.6. Statistical analysis

For each categorical variable, the results will be summarized by frequencies and percentages. For each continuous variable, the results will be summarized by descriptive statistics such as median, range, and interquartile range or by means, standard deviations and 95% confidence intervals (CIs). For proportions, point estimates and exact 95% confidence intervals will be calculated. For time to event endpoints, Kaplan-Meier estimates at selected time points and corresponding curves will be presented. Time to event is derived relative to the first study treatment administration. Laboratory values will be expressed as the absolute values and as grading (ordinal categorical variables) according to NCI CTCAE v 4.03.

Treatment-emergent AE (AEs starting after the administration of study treatment and up to study completion) will be summarized by system organ class and preferred term. Grading will be presented by type and grade in tables showing frequency and percentage of the within-patient worst grades. In addition, grade ≥3 AEs will be summarized separately. Full analysis details will be outlined in the statistical analysis plan (SAP).

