# **4.2.1.INTRACRANIAL RESPONSE DURATION**

Table 43: Intracranial Response Duration (months) ITT

Duration of response (months)	
_ N	
Mean (95%CI)	
SD	
Median (95%CI)	
Range	

Table 44: Intracranial Response Duration (months) PP

Duration of response (months)	
N	
Mean (95%CI)	
SD	
Median (95%CI)	
Range	

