# 4.6. INTRACRANIAL PROGRESSION-FREE SURVIVAL (IPFS).

Intracranial Progression-free survival (PFS), defined as the time from inclusion (first dose of treatment) until intracranial tumour progression (RECIST 1.1) or death. Patients without any of the previous events are censored at the date of the last available tumor assessment.

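### Intracranial duration of response counts only cancer deaths while iPFS counts any death, with no censoring or cause-attribution rule; if other deaths are censored in Kaplan-Meier, the duration is biased upward

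*Combined protocol and SAP*

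**What the plan says.** Protocol 10.2 starts iDOR at the first documented CR or PR, in patients who respond before local treatment, and ends it at "first documented intracranial progression or death due to underlying cancer". The next definition in that section, iPFS, ends at "the first documented intracranial disease progression or death due to any cause, whichever occurs first". SAP 4.6 runs iPFS "until intracranial tumour progression (RECIST 1.1) or death", with no restriction on cause. For survival, "OS is calculated as the time from date of inclusion to date of death due to any cause". Of these three endpoints, iDOR alone restricts the cause of death.

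The censoring rules in 10.2 are written for iPFS. For patients alive without progression, "date of progression will be censored at the date of the last follow-up". Nothing equivalent is given for iDOR.

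On method, protocol 10.6 states: "For time to event endpoints, Kaplan-Meier estimates at selected time points and corresponding curves will be presented". SAP 4.2.1 contains only table shells, beginning with "Table 43: Intracranial Response Duration (months) ITT". Their rows are N, mean, SD, median and range. There is no definition, no row for censored patients and no Kaplan-Meier label.

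Neither document has a rule for attributing cause of death. Under protocol 8.2(f), patients who move to another treatment have no formal follow-up beyond the date of death. SAP Tables 51 to 53 hold death status and date but no cause.

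**The concern.** A responder who dies without intracranial progression, from toxicity or an unrelated illness, has an iPFS event and an OS event on that day but no iDOR event. The plan does not say what happens to that patient's duration. Under Kaplan-Meier the usual default for a non-event is censoring, which treats the patient as if still at risk of progressing. Such censoring is informative and can only raise the curve.

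The restriction has no evident purpose. It does not isolate intracranial control, because a death from extracranial melanoma still counts. It also makes the endpoint depend on a judgement of cause, made in an open-label single-arm trial without adjudication and partly without the data to support it.

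What is at stake is the reported length of response. That figure matters because the trial rationale (protocol section 3) asks whether local therapy after a partial response could prolong responses.

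**Working it through.** **Inputs from the documents.** Event definitions for iDOR, iPFS and OS (protocol 10.2; SAP 4.6); Kaplan-Meier for time-to-event endpoints (protocol 10.6); 63 planned patients (synopsis); response rates of 40% and 60% (protocol 10.1).

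**Assumed inputs.** Exponential durations; an any-cause median iDOR, m, of 10 or 6 months; a share f of iDOR-ending events that are non-cancer deaths. The documents give none of these.

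**Step 1: the plan's own figure.** There is none for iDOR. The one design figure is the cohort 1 sample size. It reproduces as ((1.645·√(0.4·0.6) + 0.842·√(0.6·0.4))/0.2)² = 37.1, rounded up to 38, and 38/0.8 = 47.5, rounded up to 48. iDOR does not enter it.

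**Step 2: direction.** The Kaplan-Meier curve is a product of factors (1 − d/n) over event times. Reclassifying a death from event to censored sets its factor to 1 and leaves the later risk sets unchanged. The resulting curve can equal the any-cause curve or lie above it, but never below.

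**Step 3: size.** The total hazard is λ = ln 2/m. Censoring a share f of the events leaves hazard λ(1−f), so the Kaplan-Meier median is m/(1−f) and the 12-month rate is exp(−12λ(1−f)). For m = 10 and f = 5%: 10/0.95 = 10.5 months, and exp(−12 × 0.0693 × 0.95) = 45.4%.

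| f | 1/(1−f) | Median, m = 10 | 12-month rate, m = 10 | Median, m = 6 |
|---|---|---|---|---|
| 0 | 1.00 | 10.0 | 43.5% | 6.0 |
| 3% | 1.03 | 10.3 | 44.6% | 6.2 |
| 5% | 1.05 | 10.5 | 45.4% | 6.3 |
| 10% | 1.11 | 11.1 | 47.3% | 6.7 |

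**Step 4: sample size of responders.** 63 × 0.40 = 25.2 and 63 × 0.60 = 37.8, so take 25 and 38 responders. A simulation of 4,000 trials with m = 6 and follow-up limits spread evenly from 22 to 58 months gave these typical medians:

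- 25 responders: 6.0 months with any-cause death; 6.4 (f = 5%) and 6.7 (f = 10%) with other deaths censored.
- 38 responders: 6.2 months with any-cause death; 6.3 and 6.7 with other deaths censored.

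If every responder has an iDOR-ending event, f = 3% to 10% means between 25 × 0.03 = 0.8 and 38 × 0.10 = 3.8 deaths.

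**Step 5: the other reading.** SAP Tables 43 and 44 could be filled with plain summaries of observed durations. If a duration ends at death whatever the cause, the restriction has no effect. If such patients are dropped and cause is unrelated to duration, the simulated mean stays at about 8.1 months. The upward shift therefore depends on censoring in Kaplan-Meier.

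**The case against.** The strongest objection is that the plan never says these deaths are censored. A reader might infer that toxic or unexplained deaths are treated as ongoing responses and so lengthen iDOR. The documents do not support that as a statement of fact. Protocol 10.6 names Kaplan-Meier in general terms, but SAP 4.2.1 and Table 167 show a descriptive layout, whereas the SAP's iPFS tables have a row for censored patients and its OS tables are labelled Kaplan-Meier. A death of unknown cause in metastatic melanoma could just as well be attributed to the cancer. This objection stands, and it makes the bias conditional.

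A reader might also infer that the definition favours the regimen by concealing toxic deaths. That does not follow. There is no comparator, iDOR has no threshold or decision rule, and such deaths remain events in OS and iPFS and appear in the safety tables and the SAE listing.

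A cause-restricted endpoint can be a deliberate choice, and the shifts in the table are smaller than one 8-week imaging interval (56/30.4 = 1.8 months). Both points limit the importance of the matter. Neither supplies the missing censoring and attribution rules or a reason for the mismatch.

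**Conclusion.** The mismatch is established from the text: iDOR restricts the cause of death, iPFS and OS do not, and the SAP neither defines iDOR nor resolves the difference. The missing censoring and attribution rules leave the result open to a choice made after the data are seen.

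The upward bias is conditional on non-cancer deaths being censored in a Kaplan-Meier analysis. Under constant hazards the median then rises by about 3%, 5% or 11% for shares of 3%, 5% or 10%. The shares and the underlying medians are assumptions, so the actual size cannot be derived from the documents. Under a plain descriptive summary with durations ending at death, the shift is zero.

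This is a minor point about a secondary endpoint. The primary intracranial response rate and the sample size of 38 evaluable and 48 enrolled are untouched.

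**What to change.** In protocol 10.2, define the iDOR event as first documented intracranial progression or death from any cause, as for iPFS. Repeat the definition in SAP 4.2.1. State there that Tables 43 and 44 use Kaplan-Meier estimation and that living, progression-free responders are censored at the last tumour assessment, which is the rule SAP 4.6 already uses for iPFS. Add rows for events and censored patients, and drop the SD.

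Report the cancer-death-only version as a sensitivity analysis, with a written rule for attributing cause that covers unknown causes, and list responders' deaths by cause.

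The cost is one phrase in the protocol, a short SAP paragraph and possibly a slightly shorter reported duration. The main analysis needs no new data and no longer needs cause of death. SAP 3.5 reports patients still on treatment at database closure, so the SAP text appears to follow that closure. If the change is made after it, it should be declared as such, with both versions shown.
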